#### 11.1.4 Duration of Response

Duration of overall response: The duration of overall response is measured from the time measurement criteria are met for CR or PR (whichever is first recorded) until the first date that recurrent or progressive disease is objectively documented (taking as reference for progressive disease the smallest measurements recorded since the treatment started, or death due to any cause. Participants without events reported are censored at the last disease evaluation).

Duration of overall complete response: The duration of overall CR is measured from the time measurement criteria are first met for CR until the first date that progressive disease is objectively documented, or death due to any cause. Participants without events reported are censored at the last disease evaluation.

Duration of stable disease: Stable disease is measured from the start of the treatment until the criteria for progression are met, taking as reference the smallest measurements recorded since the treatment started, including the baseline measurements.

#### 11.1.5 Clinical Benefit rate

Clinical benefit rate: defined as CR, PR and stable disease (SD)  $\geq$  27 weeks.

### 11.2 Antitumor Effect – Hematologic Tumors

N/A

### 11.3 Other Response Parameters

#### 11.3.1 Definition of Tumor Response Using Immune-Related Response Criteria (irRECIST)

The sum of the product of the longest diameter of lesions (SPD) at tumor assessment using the immune-related response criteria (irRECIST) for progressive disease incorporate the contribution of new measurable lesions. Each net Percentage Change in Tumor Burden per assessment using irRC criteria accounts for the size and growth kinetics of both old and new lesions as they appear.

##### 11.3.1.1 Impact of New Lesions on irRECIST

New lesions in and of themselves do not qualify as progressive disease. However, their contribution to total tumor burden is included in the SPD which in turn feeds into the irRECIST criteria for tumor response. Therefore, new non-measurable lesions will not

discontinue any subject from the study.

#### 11.3.1.2 Definition of Target Lesions Response Using irRECIST

- **irRECIST Complete Response (irRECIST CR):** Complete disappearance of all target lesions. This category encompasses exactly the same subjects as “CR” by the mWHO criteria.
- **irRECIST Partial Response (irRECIST PR):** Decrease, relative to baseline, or 50% or greater in the sum of the products of the two largest perpendicular diameters of all target and all new measurable target lesions (i.e., Percentage Change in Tumor Burden). Note: the appearance of new measurable lesions is factored into the overall tumor burden, but does not automatically qualify as progressive disease until the SBD increases by  $\geq 25\%$  when compared to SPD at nadir.
- **irRECIST Stable Disease (irRECIST SD):** Does not meet criteria for irRECIST RC or irPR, in the absence of progressive disease.
- **irRECIST Progressive Disease (irRECIST PD):** At least 25% increase Percentage Change in Tumor Burden (i.e. taking SPD of all target lesions and any new lesions) when compared to SPD at nadir.

#### 11.3.1.3 Definition of Non-Target Lesions Response Using irRECIST

- **irRECIST Complete Response (irRECIST CR):** Complete disappearance of all non-target lesions. This category encompasses exactly the same subjects as “CR” by the mWHO criteria.
- **irRECIST Partial Response (irRECIST PR) or irRECIST Stable Disease (irRECIST SD):** Non-target lesion(s) are not considered in the definition of PR; these terms do not apply.
- **irRECIST Progressive Disease (irRECIST PD):** Increases in number or size of non-target lesion(s) does not constitute progressive disease unless/until the Percentage Change in Tumor Burden increases by 25% (i.e. the SPD at nadir of the target lesions increases by the required amount).

#### 11.3.1.4 Definition of Overall Response Using irRECIST

Overall response using irRECIST will be based on these criteria:

- **Immune-Related Complete Response (irRECIST CR):** Complete disappearance of all tumor lesions (target and non-target) together with no new measurable/unmeasurable lesions for at least 4 weeks from the date of documentation of complete response.
- **Immune-Related Partial Response (irRECIST PR):** The sum of the products of the two largest perpendicular diameters of all target lesions is measured and captured as the SPD baseline. At each subsequent tumor assessment, the SPD of the two largest perpendicular diameters of all target lesions and of new measurable lesions are added together to provide the Immune Response Sum of Product Diameters (irRECIST SPD). A decrease, relative to baseline, of the irRECIST SPD compared to the previously SPD baseline of 50% or greater is considered an irRECIST PR.

- **Immune-Related Stable Disease (irRECIST SD):** irRECIST SD is defined as the failure to meet criteria for immune complete response or immune partial response, in the absence of progressive disease
- **Immune-Related Progressive Disease (irRECIST PD):** It is recommended in difficult cases to confirm PD by serial imaging. Any of the following will constitute PD:
  - At least 25% increase in the SPD of all target lesions over nadir SPD calculated for the target lesions.
  - At least 25% increase in the SPD of all target lesions and new measurable lesions (irRECIST SPD) over the baseline SPD calculated for the target lesions.

Criteria for determining overall response by irRECIST are summarized as follows:

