### 11.1.2 Disease Parameters

**Measurable disease.** Measurable lesions are defined as those that can be accurately measured in at least one dimension (longest diameter to be recorded) as  $\geq 20$  mm by

chest x-ray or  $\geq 10$  mm with CT scan, MRI, or calipers by clinical exam. All tumor measurements must be recorded in millimeters (or decimal fractions of centimeters).

Note: Tumor lesions that are situated in a previously irradiated area are not considered measurable.

Malignant lymph nodes. To be considered pathologically enlarged and measurable, a lymph node must be  $\geq 15$  mm in short axis when assessed by CT scan (CT scan slice thickness recommended to be no greater than 5 mm). At baseline and in follow-up, only the short axis will be measured and followed.

Non-measurable disease. All other lesions (or sites of disease), including small lesions (longest diameter  $< 10$  mm or pathological lymph nodes with  $\geq 10$  to  $< 15$  mm short axis), are considered non-measurable disease. Bone lesions, leptomeningeal disease, ascites, pleural/pericardial effusions, lymphangitis cutis/pulmonitis, inflammatory breast disease, abdominal masses (not followed by CT or MRI), and cystic lesions are all considered non-measurable.

Note: Cystic lesions that meet the criteria for radiographically defined simple cysts should not be considered as malignant lesions (neither measurable nor non-measurable) since they are, by definition, simple cysts.

'Cystic lesions' thought to represent cystic metastases can be considered as measurable lesions, if they meet the definition of measurability described above. However, if non-cystic lesions are present in the same participant, these are preferred for selection as target lesions.

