Target lesions. All measurable lesions up to a maximum of 2 lesions per organ and 5 lesions in total, representative of all involved organs, should be identified as **target lesions** and recorded and measured at baseline. Target lesions should be selected on the basis of their size (lesions with the longest diameter), be representative of all involved organs, but in addition should be those that lend themselves to reproducible repeated measurements. It may be the case that, on occasion, the largest lesion does not lend itself to reproducible measurement in which circumstance the next largest lesion which can be measured reproducibly should be selected. A sum of the diameters (longest for non-nodal lesions, short axis for nodal lesions) for all target lesions will be calculated and reported as the baseline sum diameters. If lymph nodes are to be included in the sum, then only the short axis is added into the sum. The baseline sum diameters will be used as reference to further characterize any objective tumor regression in the measurable dimension of the disease.

Non-target lesions. All other lesions (or sites of disease) including any measurable lesions over and above the 5 target lesions should be identified as **non-target lesions** and should also be recorded at baseline. Measurements of these lesions are not required, but the presence, absence, or in rare cases unequivocal progression of each should be noted throughout follow up.

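### irRECIST progression for target plus new lesions is measured from nadir in one subsection and from baseline in another, and the rules on which diameters to record conflict

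*Combined protocol and SAP*

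**What the plan says.** **Progression reference.** Section 11.3.1.2 counts a rise of at least 25% in the SPD of target lesions and "any new lesions) when compared to SPD at nadir" as irRECIST progression. Section 11.3.1.4 lists two criteria, either of which is enough. The first is a 25% rise in the target SPD over the target nadir. The second is a 25% rise in the SPD of target plus new measurable lesions "over the baseline SPD calculated for the target lesions". The summary table that follows has a single percent-change column with 25% cut-offs and does not say what the change is measured from.

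**Which new lesions count.** The progression definition in 11.3.1.2 includes new lesions of any kind. Section 11.3.1.4 and the table include only measurable ones.

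**Which diameters are taken.** Section 11.3.1.4 states: "The sum of the products of the two largest perpendicular diameters of all target lesions is measured and captured as the SPD baseline". The introduction to 11.3.1 describes the quantity differently: "The sum of the product of the longest diameter of lesions (SPD". Section 11.1.2 works with one dimension per lesion ("longest diameter to be recorded"). It says of malignant nodes: "At baseline and in follow-up, only the short axis will be measured and followed". For the baseline total it says: "A sum of the diameters (longest for non-nodal lesions, short axis for nodal lesions) for all target lesions will be calculated and reported".

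**Use.** Sections 1.3, 13.1 and 13.5 make PFS, ORR, CBR and DOR by irRECIST secondary endpoints. Under 13.5, ORR and CBR by irRECIST are compared between arms at one-sided 0.1. PFS by irRECIST is estimated with a confidence interval and not tested. DOR is summarised descriptively.

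**The concern.** Section 11.3.1.1 says that new lesions are not progression in themselves and act only through the SPD. How they enter the SPD, and what the SPD is compared with, is therefore the working part of the criterion. If two subsections answer that differently, the progression date of a responder with new lesions depends on which one the programmer follows. The trial is open label, so leaving that choice until data are in hand invites a choice influenced by results. The measurement conflict raises a second problem: a single recorded diameter does not determine a product of two.

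**Working it through.** The plan gives no figure to reproduce here. The check sets the rules side by side and applies them to illustrative SPD values, which are assumptions.

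**Notation.** B = baseline target SPD, n = nadir SPD, T = current target SPD, N = current SPD of new measurable lesions.

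- Rule in 11.3.1.2: progression if (T + N)/n ≥ 1.25.
- Rule in 11.3.1.4: progression if T/n ≥ 1.25, or if (T + N)/B ≥ 1.25.

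**No new lesions (N = 0).** The nadir cannot exceed baseline, so T/B ≥ 1.25 implies T/n ≥ 1.25. Both rules reduce to T/n ≥ 1.25 and always agree.

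**New lesions after shrinkage.** Take B = 1000, an earlier scan with targets at 400 and no new lesions (so n = 400), and a current scan with T = 400 and N = 200.

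- 11.3.1.2: 600/400 = 1.50, or +50%: progression.
- 11.3.1.4, first criterion: 400/400 = 1.00, or 0%: not met.
- 11.3.1.4, second criterion: 600/1000 = 0.60, or -40%: not met, so no progression.

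**Size of the disagreement.** Hold targets at nadir with B = 1000. Progression then needs N ≥ 0.25n under 11.3.1.2, and N ≥ 1250 - n under 11.3.1.4.

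| Nadir n | N needed, 11.3.1.2 | N needed, 11.3.1.4 |
|---|---|---|
| 1000 | 250 | 250 |
| 800 | 200 | 450 |
| 500 | 125 | 750 |
| 400 | 100 | 850 |

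The rules coincide when nothing has shrunk and diverge as shrinkage deepens. At n = 500 the gap is 750/125 = 6-fold.

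**Which nadir.** 11.3.1.2 does not say whether its nadir is that of the targets alone or of the total. If it is the total, the disagreement can reverse. Take B = 1000, target nadir 400, total nadir 700, now T = 500 and N = 300. 11.3.1.2 gives 800/700 = +14%, not progression. The first criterion of 11.3.1.4 gives 500/400 = +25%, progression.

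**One diameter against two (single lesion).**

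- Longest diameter 20 to 23 mm: 23/20 = 1.15. If the other diameter is unchanged, the product rises 15%: not progression. If it grows in proportion, 1.15² = 1.3225, or +32%: progression.
- Longest diameter 20 to 14 mm: 14/20 = 0.70. If the other diameter is unchanged, the product falls 30%: not a partial response. If it shrinks in proportion, 0.70² = 0.49, or -51%: partial response.

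**Endpoints reached.** PFS and DOR by irRECIST use the progression date. CBR uses it where stable disease has to last 27 weeks. Those patients have shrunk by less than 50%, as in the n = 800 row (200 against 450). Partial response is set against baseline in both subsections, so the reference conflict does not move the response threshold. ORR is exposed mainly through the diameters.

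**The case against.** Several stronger readings are tempting, and the documents do not support them.

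- *The second diameter is not collected.* A reader might infer this from 11.1.2. But 11.3.1.4 says the two-diameter SPD is captured at baseline and computed again at each assessment, and 11.1 may be meant only for RECIST 1.1. The case report form is not in the documents. What stands is that the two sections give unreconciled instructions, most plainly for nodes.
- *After halving, progression falls at 62.5% of baseline under one rule (0.5 × 1.25) and at 125% under the other.* This is not general. If the targets themselves regrow, the first criterion of 11.3.1.4 already gives progression at 62.5%. The gap needs new measurable lesions to supply the increase. Nor do the two criteria inside 11.3.1.4 contradict each other, because they apply to different sums. The conflict is between 11.3.1.2 and the second criterion of 11.3.1.4.
- *The immune criterion is wrongly stricter than RECIST.* Under uniform growth, +25% in product is √1.25 = 1.118, or +11.8% in diameter, while +20% in diameter is 1.2² = 1.44, or +44% in product. That is a property of any bidimensional criterion. Sections 11.3.1.1 and 11.3.1.3 place the tolerance in new lesions and non-target growth. Nothing promises more leniency on target growth.

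It can also be argued that 11.3.1.4, as the overall-response section, governs. No text says so. The 11.3.1.2 definition itself includes new lesions, and the table takes the target classification as an input.

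The impact is limited, and that part of the objection stands: these are secondary endpoints, and PFS by irRECIST carries no test.

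**Conclusion.** The point holds in a bounded form. For target plus new lesions, 11.3.1.2 and 11.3.1.4 set progression against different references, and the table does not settle it. One scan can therefore be progression or not (+50% against -40% in the worked case). The conflict is confined to patients with new measurable lesions, and under the illustrated conditions (targets held at nadir) it grows with prior shrinkage. How many of the 88 patients that would be cannot be estimated from the documents. The difference between any new lesions and measurable ones adds ambiguity.

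The measurement rules in 11.1.2 and 11.3 also conflict, and the actual practice is unknown. PFS, DOR and CBR by irRECIST are not uniquely defined as written, and ORR by irRECIST is exposed mainly through measurement. It would go too far to say that no irRECIST endpoint can be derived. The primary RECIST 1.1 analysis and the sample size are untouched. The SPD values are illustrative; the contradiction does not depend on them.

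**What to change.** 1. Use one progression reference for target plus new measurable lesions in 11.3.1.2, 11.3.1.4 and the table. Nadir is the natural choice, since 11.3.1.2 and the first criterion of 11.3.1.4 already use it. State whether the nadir is of the total or of the targets alone.
2. Use one new-lesion rule in all three places, and name the reference in the table's percent-change column.
3. Choose one measurement scale. Either state in 11.1.2 that the second perpendicular diameter is recorded for target and new lesions, including nodes, or, if it is not recorded, restate 11.3 on the unidimensional sum.

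Replacing the cut-offs with RECIST's -30% and +20%, or making confirmation of progression mandatory, is not needed to remove the contradiction. Either would redefine the endpoints. If the unidimensional route is taken, its cut-offs must be chosen and justified openly.

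Cost: items 1 and 2 are protocol wording. Item 3 is wording if the second diameter is already captured. If it is not, the two-diameter route adds a measurement per lesion and possibly re-reading of earlier scans, while the unidimensional route changes the criterion. None of this alters the primary analysis. It should be settled before any irRECIST endpoint is derived.

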**Immune-Related Response Criteria Definitions**

Target Lesion Definition	Non-Target Lesion Definition	New Measurable Lesions	New Unmeasurable Lesions	Percent change in tumor burden (including measurable new lesions when present)	Overall irRC Response
Complete Response	Complete Response	No	No	-100%	irCR
Partial Response	Any	Any	Any	≥ -50%	irPR
				<-50% to <+25%	irSD
				>+25%	irPD
Stable Disease	Any	Any	Any	<-50% to <+25%	irSD
				>+25%	irPD
Progressive Disease	Any	Any	Any	≥+25%	irPD

#### 11.3.1.5 Immune-Related Best Overall Response Using irRECIST (irRECIST BOR)

irRECIST BOR is the best confirmed overall response over the study as a whole, recorded between the date of first dose until the last tumor assessment before subsequent therapy (except for local palliative radiotherapy for painful bone lesions) for the individual subject in the study. For the assessment of irBOR, all available assessments per subject are considered.

irRECIST CR or irRECIST PR determinations included in the irRECIST BOR assessment must be confirmed by a second (confirmatory) evaluation meeting the criteria for response and performed no less than 4 weeks after the criteria for response are first met.

## 12. DATA REPORTING / REGULATORY REQUIREMENTS

Adverse event lists, guidelines, and instructions for AE reporting can be found in Section 7.0 (Adverse Events: List and Reporting Requirements).

## **12.1 Data Reporting**

### **12.1.1 Method**

ODQ will collect, manage, and perform quality checks on the data for this study.

### **12.1.2 Responsibility for Data Submission**

Investigative sites within DF/HCC or DF/PCC are responsible for submitting data and/or data forms to ODQ according to the schedule set by ODQ.

## **12.2 Data Safety Monitoring**

The DF/HCC Data and Safety Monitoring Board (DSMB) will review and monitor study progress, toxicity, safety and other data from this study. The board is chaired by a medical oncologist from outside of DF/HCC and has external and internal representation. Information that raises any questions about participant safety or protocol performance will be addressed by the Overall PI, statistician and study team. Should any major concerns arise, the DSMB will offer recommendations regarding whether or not to suspend the study.

The DSMB will meet twice a year to review accrual, toxicity, response and reporting information. Information to be provided to the DSMB may include: participant accrual; treatment regimen information; adverse events and serious adverse events reported by category; summary of any deaths on study; audit results; and a summary provided by the study team. Other information (e.g. scans, laboratory values) will be provided upon request.

## **12.3 Multicenter Guidelines**

N/A

## **12.4 Collaborative Research and Future Use of Data and Biospecimens**

Tissue, blood, stool, bodily fluids, and other materials derived from these will be collected in this study to analyze genes, DNA, RNA, proteins and cells for the study's correlative endpoints and potential future research, utilizing new types of biomarker testing as it becomes available.

These samples and any data generated as a part of these clinical trials may be used for future research studies and may be provided to collaborating investigators both within and outside of the DF/HCC for either correlative endpoints or secondary use. Samples and data may be shared with outside non-profit academic investigators, as well as with for-profit pharmaceutical investigators or commercial entities, with whom we collaborate. When samples or data are sent to collaborators and when any research is performed on them, all information will be identified with a code, and will not contain any PHI, such as name, birthday, or MRNs.

In order to allow the greatest amount of research to be performed on the specimens and information generated as a part of this trial, researchers in this study may share results of genetic sequencing with other scientists. De-identified specimen or genetic data may be placed into one of more publicly-accessible scientific databases, such as the National Institutes of Health's Database for Genotypes and Phenotypes (dbGaP). The results from the correlative research on this study will be shared with these public databases. Through such databases, researchers from around the world will have access to de-identified samples or data for future research. More detailed information, beyond the public database, may only be accessed by scientists at other research centers who have received special permission to review de-identified data.

## **13. STATISTICAL CONSIDERATIONS**

### **13.1 Study Design/Endpoints**

This is a randomized phase II open label study of eribulin mesylate +/- Pembrolizumab for patients with metastatic HR positive breast cancer treated with 0-2 line of chemotherapy. Eighty-eight patients will be randomized (1:1) to eribulin mesylate with pembrolizumab or eribulin mesylate. Patients randomized to eribulin mesylate monotherapy will have the option to receive pembrolizumab monotherapy at time of progression.

The primary endpoint is PFS, defined as the time from study randomization to disease progression per RECIST 1.1 or death due to any cause, whichever occurred first. Patients alive without disease progression are censored at the date of last disease evaluation. The primary objective is to compare PFS of patients randomized to receive eribulin mesylate in combination with pembrolizumab (Arm A) versus those randomized to receive eribulin mesylate monotherapy (Arm B).

Secondary endpoints include PFS per irRECIST criteria, ORR per RECIST 1.1 and irRECIST, DOR, CBR, OS, safety and tolerability. For the patients randomized to the eribulin monotherapy arm who elect to receive the combination after progression, we will also perform an exploratory analysis of all clinical endpoints for patients using measurements at progression on monotherapy as the baseline tumor assessment.

